9.4.3.1 Collection of Specimens

No additional tumor tissue will be obtained beyond that initially obtained for clinical purposes, but no longer needed for those purposes.

# Tumor Tissue

For each subject:

- Obtain 10 tumor tissue sample (slides) for the following time points:
  - a) Baseline
  - b) End of study treatment (if available)

9.4.3.2 Handling of Specimens

# Tumor Tissue

- Sections should be freshly cut for IHC staining.
- Use positively charged microscope slides, such as Superfrost Plus Fisher Catalog #22-034-979 or #12-550-15.
- Cut 10 unstained slides with section thickness of 5 microns.
- Slide drying should be performed at 37°C overnight.
- Storage of cut slides at room temperature should ideally not exceed more than 7 days.
- Longer-term storage should be at 4°C, with slide boxes carefully parafilmed to prevent moisture entering the slide box.
- Mark each slide with:
  - Study Number NCI9925
  - Subject ID Number
  - Sample Type **PDL**
  - Date of Specimen
  - Corresponding Accession Number
  - Serial Number of Slide (1, 2, 3...)

9.4.3.3 Site Performing Correlative Study

IHC study will be performed in the [name] Laboratory at Washington University.

#### 9.4.4 Tumor Antigen Analysis - Biomarker for Correlation with Responses

Hypothesis: Nivolumab will enhance anti-ATLL immune responses directed against tumor antigens.

Rationale: Responses to nivolumab in solid tumors correlate with the level of mutant tumor antigens.

Preclinical and Clinical Results: See Section 2.2 for Pharmacodynamics/Biomarkers (2.2.6).

Assay Methodology: Primary tumor or leukemic blood samples and matched normal specimens (skin or CD19+ peripheral blood B cells) are obtained. Only specimens with high tumor cellularity (>75%) will be used. Tumor and skin specimens are snap frozen in liquid nitrogen after surgical resection or biopsy and stored at -80 °C. Sections of tumor are stained with hematoxylin and eosin. DNA is extracted and exon capture is performed using a human All Exon 50MB kit (Agilent) with the addition of capture probes corresponding to the entire HTLV-1 genome. Enriched exome libraries will be sequenced on the HiSeq 2500 platform (llumina) to >100X coverage. Alignment, base-quality score recalibration and duplicate-read removal are performed, germline variants excluded, mutations annotated and indels evaluated. Samples with tumor coverage  $\leq 10X$  were excluded. Medium-confidence reads (11-34X) are manually reviewed using the Integrated Genomics Viewer for sequencing of candidate mutations. Mutations between clinical groups were compared using the Mann-Whitney test.

HLA typing is performed by either low to intermediate resolution polymerase chain reactionsequence-specific primer (PCR-SSP) method or by high–resolution SeCore HLA sequencebased typing method (HLA-SBT) (Invitrogen). ATHLATES (http://www.broadinstitute.org/scientificcommunity/science/projects/viralgenomics/athlates)3 is also used for HLA typing and confirmation. The bioinformatic tool NAseek is used which performs two functions: translation of stretches surrounding each mutation, and comparison between the resulting peptides for homology. First, NASeek translates all mutations in exomes so strings of 17 amino acids are generated for the predicted wild type and mutant, with the amino acid resulting from the mutation is situated centrally. Next, to evaluate MHC Class I binding, wild type and mutant nonamers containing the tetrapeptides common to the complete responders are input into NetMHC v3.4 (http://www.cbs.dtu.dk/services/NetMHC/) or RANKPEP (http://imed.med.ucm.es/Tools/rankpep.html) for patient-specific HLA types, using a sliding window method. These programs generate a predicted MHC Class I binding strength. Finally, NAseek assesses for similarity between nonamers that are predicted to be presented by patient-specific MHC Class I. The logo plot of the amino acid frequencies is executed using Weblogo (http://weblogo.berkeley.edu/logo.cgi) with default parameters. In order to further narrow down the predicted nonamers for testing in vitro, nonamers were also evaluated for putative binding to the T cell receptor using the IEDB immunogenicity predictor with patientspecific HLA types (http://tools.immuneepitope.org/immunogenicity/) and CTLPred (http://www.imtech.res.in/raghava/ctlpred/). To evaluate homology to known pathogens' antigens, conserved tetrapeptides are analyzed using Immune Epitope Database (www.iedb.org) and assessed as substrings of immunogens in the database for a positive T cell response in *Homo sapiens* host. The "neoantigen signature" is generated from the nonamers containing the peptides common to patients with long-term benefit. Standard methods for signature derivation using unsupervised hierarchical clustering followed by logistic regression are used to determine predictive models based solely on the discovery set data. We will perform simulation/permutation testing to demonstrate that the neoantigen signature is highly unlikely to result from chance. To assess the null hypothesis that the signature is due to chance, 5 distinct simulation models are evaluated, three with new datasets and two using permutations of our dataset. The simulations are executed using (a) nonamers drawn from the SwissProt database (b) mutations from the TCGA T-cell lymphoma dataset (c) randomly generated nonamers (d) redistribution of the mutations found in our data and (e) reordering of the 9 amino acids within each nonamer predicted to be presented in our dataset. In each simulation, the nonamers are distributed randomly, and in proportion to our data (for example, if an actual sample harbored 150 nonamers predicted to bind MHC Class I, then the "virtual" sample is assigned 150 nonamers). Simulation testing is then conducted by applying the same iterative model used on the actual data applied to this virtual dataset, and repeating this process 1,000 times, recording the frequency of signatures greater than the actual signature to determine the p value. P value was calculated as the proportion of iterations with a signature greater that correctly classified segregation of the clinical cohorts, divided by the 1,000 iterations.

Mann-Whitney test is used to compare non-synonymous exonic mutational burden between clinical groups. Log-Rank test was used to compare the Kaplan-Meier curves for overall survival in the discovery and validation sets. As described above, simulation testing was used with the null hypothesis that all tetrapeptides contribute equally to clinical benefit to determine if a signature of the size we found happened by chance.

Investigator's Experience and Competence with the Assay: [name], the Principal Investigator, has used this assay in a previous report [55], and has funding for these studies PO1 100730, R01 CA63417, and P50 CA094056

Justification for Number of Patients and Specimens: Tumor samples will be obtained at baseline and end of study time point. A skin biopsy is obtained at baseline, at the same time as the bone marrow biopsy to provide germline DNA not contaminated with PBMCs.

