#### 13.2 Study Design

At least 20 evaluable patients will be enrolled for this study. Evaluable patients will be those patients who received study medication. The sample size of 20 patients is based on Simon's Optimal 2-stage design, with the assumption that an overall response rate of 40% is the minimum response rate that would be considered for further analysis of this approach, compared to a rate of 10% under null hypothesis. Thus, 20 subjects are required to with a one-side type 1 error rate of 5% and a power of 90%. If 1 or fewer responses are seen among the first 9 subjects enrolled, the trial is stopped early for futility. In contrast, if 2 or more responders are observed out of the 9 patients in the first stage, additional 11 patients will be enrolled in the 2nd stage. In a multicenter study such as this, however, it is difficult for a trial to reach the planned sample exactly. The investigators would not turn away patients who have already been approached for participation just because the number of patients needed has been met. Therefore, we adopted a flexible Phase II design (Chen and Ng 1998) to allow the actual number at final stage to deviate slightly from

what is planned. Due to the expected relatively low accrual rate, we expect that the interim analysis could be performed at the designed sample size. Only the decision boundaries at the 2nd-stage are determined following Chen and Ng's flexible design and programed by the study statistician [57]. That is, if 5 or more responders are observed out of 20-23 patients, or 6 or more responders are observed out of 24-25 patients, we would conclude that preliminary evidence for efficacy exists and that further investigation of the treatment is warranted.

The interim analysis will be based upon independent review of response, with a minimum time frame of 2 months for the interim analysis. Accrual will not be halted during the interim analysis.

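### Section 9.4.4 plans a log-rank test in a validation set the trial does not have; run in the patients who defined the neoantigen signature, its p-value is not interpretable

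*Combined protocol and SAP*

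**What the plan says.** The analysis sits in Section 9.4.4 of the combined protocol and SAP, under the exploratory and ancillary studies of Section 9.4. The signature "is generated from the nonamers containing the peptides common to patients with long-term benefit". The same section says that the models are derived from the discovery set alone. It then gives the survival analysis: "Log-Rank test was used to compare the Kaplan-Meier curves for overall survival in the discovery and validation sets".

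Five simulation models are planned as a guard against chance. Three use new data: peptides from a protein database, mutations from a public T-cell lymphoma dataset, and random peptides. Two use the trial's own data: (d) redistributes the observed mutations, and (e) reorders the amino acids within each peptide. The derivation is repeated 1,000 times, "recording the frequency of signatures greater than the actual signature to determine the p value". A second sentence describes the p-value differently: "P value was calculated as the proportion of iterations with a signature greater that correctly classified segregation of the clinical cohorts".

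On size, Section 13.2 says "At least 20 evaluable patients will be enrolled for this study", with final decision rules for 20 to 25. Section 13.3 refers back to Section 9 for the detail of the correlative analyses, so it adds nothing here.

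**The concern.** A signature made of features shared by patients who did well will, by construction, tend to mark patients who did well. Testing survival by that signature in the same patients partly tests the outcome against itself. The usual protection is a second set of patients that played no part in the derivation. Section 9.4.4 writes as if such a set exists, but the plan gives it no source, size or allocation rule.

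Two further terms are open. Long-term benefit is not defined, and an earlier step in 9.4.4 selects peptides shared by complete responders, which is a different group. The groups compared by the log-rank test are also not stated; I take them to be patients with and without the signature. At stake is a survival-predictive signature, reported with a small p-value, that may reflect only how it was built.

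**Working it through.** **1. The plan's own figure.** "The sample size of 20 patients is based on Simon's Optimal 2-stage design", with null and target response rates of 10% and 40%. Exactly, the chance of declaring activity at N = 20 is the sum over x = 2 to 9 of P(X1 = x) × P(X2 ≥ 5 − x), with X1 ~ Bin(9, p) and X2 ~ Bin(11, p). This gives 0.0349 at p = 0.10 and 0.9018 at p = 0.40, so N = 20 and 90% power reproduce. They concern response only; no events, alpha or power are stated for the log-rank test.

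The chance of stopping at stage 1 is 0.9^9 + 9 × 0.1 × 0.9^8 = 0.387 + 0.387 = 0.775 at a 10% response rate, and 0.6^9 + 9 × 0.4 × 0.6^8 = 0.010 + 0.060 = 0.071 at 40%. The signature may therefore rest on far fewer than 20 patients. Section 9.4.4 also accepts only specimens with more than 75% tumor cellularity.

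**2. Same patients, benefit defined by survival.** Assumed, not in the documents: 20 patients, exponential survival with median 8 months, benefit = survival of 6 months or more, peptides carried independently of outcome. Signature = peptides present in at least 2 benefit patients and in no other patient. Two-group log-rank at 5%, 2,000 null trials per setting:

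| Candidate peptides | Carriage | p < 0.05 |
|---|---|---|
| 100 | 10% | 95.6% |
| 100 | 20% | 92.4% |
| 500 | 10% | 99.9% |
| 500 | 20% | 99.9% |

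The Monte Carlo standard error at 92.4% is √(0.924 × 0.076 / 2,000) = 0.6 percentage points. A second set of assumptions (median 6 months, censoring at 12-36 months, 2,000 or 10,000 peptides carried by 2% or 5%) gave 63-100%, and 94% or more in most settings.

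**3. Same patients, benefit defined by response.** Response is correlated with survival, and peptides still have no effect:

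| Correlation | 4 of 20 benefit | 6 of 20 | 8 of 20 |
|---|---|---|---|
| 0 | 7% | 6-7% | 6% |
| 0.5 | 22% | 9-31% | 36% |
| 0.7 | 49% | – | 70% |
| 0.9 | 87% | 35-96% | 98% |

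The middle column comes from a separate run, so the columns are not a smooth trend in the number benefiting.

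**4. With a real second set.** With the signature fixed in one part (splits 10+10, 12+8 or 13+12), the log-rank test rejects in 98-100% of null trials in the derivation part and in 5-8% in the held-out part. An internal split has little power, however. Events needed for 80% power at HR 0.5, equal groups, two-sided 5%: 4 × (1.960 + 0.842)² / (ln 0.5)² = 31.4 / 0.480 = 65.4, so 66. With 10 events, power is Φ(√10/2 × 0.693 − 1.960) = Φ(−0.864) = 19%.

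**5. The chance test.** Permuting clinical labels and repeating the whole derivation (20 patients, 4 with benefit) rejected in 3.5% of null trials; the same-patient log-rank test rejected in 100% of them. None of the five planned models is described as permuting labels. Model (d) is closest: under the assumptions of step 2, one plausible version rejected in 0-2.8% with the +1 formula and 0-5.4% with the strict greater-than rule, against 3.2-4.6% for label permutation. The algorithm for (d) is not specified.

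**6. The p-value formula.** With count c in 1,000 iterations, (c + 1)/1,001 − c/1,000 = (1,000 − c)/1,001,000, which is at most 0.001.

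**The case against.** The strongest reply is that Section 9.4.4 does separate derivation from validation: models come from the discovery set alone, so the circular analysis is not what the authors intend. That stands as intent, and no passage excludes an external cohort. But the protection works only if a second set exists, and none is identified. The sentence also applies the log-rank test to the discovery set itself, where derivation and test coincide.

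A reader might infer that a significant result is almost guaranteed. The documents do not support that without a condition. It needs benefit to be survival-based or very closely tied to survival. The section's title speaks of correlation with responses and its text of complete responders; if benefit is a response status unrelated to survival, the error rate is near nominal.

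A reader might also infer that the simulations are worthless. That is too strong: model (d) re-runs the derivation on redistributed mutations and can roughly control the chance of finding a signature. The other four are weaker, and none yields a corrected survival p-value. The missing +1 hardly matters, and the sentence that appears to divide a proportion by 1,000 again is loose wording for count over 1,000.

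Finally, the work is exploratory, Section 13.3 calls the analysis descriptive, and no trial decision depends on it. That limits the consequence but does not make the p-value readable.

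**Conclusion.** The point holds in conditional form. As the plan stands, the survival log-rank test has no independent patients to run in, and its p-value in the derivation patients is not interpretable. The range is wide because benefit is undefined: from near the nominal 5% up to 99.9%. The upper figures rest on the assumed survival distribution, cutoff, peptide pool and signature rule, and all figures rest on reading the test as signature-positive against signature-negative patients. The plan does not rule out the worst case, and even a moderate correlation of 0.5 between response and survival can inflate the error several-fold (up to 36% against 5%). This should be corrected before analysis, but it does not touch the primary endpoints.

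**What to change.** In Section 9.4.4:

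- State one definition of benefit, and reconcile complete responders with long-term benefit.
- Drop the log-rank p-value in the derivation patients. Keep a log-rank test only if a separate validation cohort is named in advance, with its size and the groups to be compared.
- Make the primary chance test a permutation of clinical-benefit labels across patients, repeating the whole derivation each time, with p = (number at least as extreme + 1)/(permutations + 1). The five simulation models can remain as supporting checks.
- Show survival by signature only with leave-one-out assignment, descriptively and labelled hypothesis-generating.

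The cost is wording and modest computing, with no new samples. The result will usually look less favourable.

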# 9.4.4.1 Collection of Specimens

No additional tumor tissue will be obtained beyond that initially obtained for clinical purposes, but no longer needed for those purposes.

# Tumor Tissue

• The same tumor tissue samples obtained for HTLV-1 studies will be used for this analysis.

# Skin

For each subject:

- Obtain a 3 or 4 mm punch biopsy of skin per standard institutional procedure at the following time point:
  - a) Baseline (at the same time as bone marrow biopsy)

# 9.4.4.2 Handling of Specimens

# Tumor Tissue

• The same tumor tissue samples obtained for HTLV-1 studies will be used for this analysis.

# Skin

- Skin punch biopsy should be flash frozen in liquid nitrogen within 2 hours of collection.
- Label each skin sample with:
  - Study Number NCI9925
  - Subject ID Number
  - Sample Type Skin
  - Collection Date
  - Collection Time

# 9.4.4.3 Shipping of Specimens

# Tumor Tissue

• The same tumor tissue samples obtained for HTLV-1 studies will be used for this analysis.

# 9.4.4.4 Site Performing Correlative Study

Studies will be performed at the [name] Laboratory at Washington University.

# 9.4.5 Protein Markers Associated with Sensitivity or Resistance to Nivolumab

Multiplex ELISA assays have been developed to analyze over 25 angiogenic, inflammatory and immune-related markers in less than 0.5 ml of plasma. Coefficients of variation for most analytes are <10%. This platform has been successfully applied to several in-house phase I and II studies, as well as several phase III, Alliance-conducted studies with bevacizumab in colorectal and other cancers at Duke University. Markers of inflammation will be analyzed in the Duke Phase I Biomarker Lab, which serves as a core lab for these analyses for the US Cooperative Group, the Alliance.

Analyses will be performed on pre-treatment and on-treatment plasma samples. Analyte levels, and changes in analyte levels, will be correlated with clinical outcome (PFS, OS). Plasma will also be evaluated for protein markers that may be associated with sensitivity or resistance to ibrutinib. These may include CRP and other markers of inflammation, including but not limited to IFN $\gamma$ , IL1 $\beta$ , IL6, sILR6R, sGP130, IL4, IL7, IL10, IL12, IL17A, IL17E, and IL23. Additional markers of proteins regulated by the PD-1/PD-L1 interaction and the IL6/JAK-STAT axis will also be assessed, including but not limited to VEGF, HER and TGF $\beta$  family members.

# 9.4.5.1 Collection of Specimens

# Plasma Collection and Processing:

• Draw one 10ml lavender top (K2EDTA) tube (BD Vacutainer, Catalog no. 366643) at the

following time points:

- a) Baseline;
- b) Every restaging;
- c) End of study treatment.
- Invert tubes 10 times to mix blood.
- Centrifuge at 4°C at 2500 x g for 15 minutes (or in accordance with centrifuge manufacturer's instructions).
- Remove plasma from each tube and transfer equally into two separate clean 15ml polypropylene tubes (or institutional equivalent).
- Repeat centrifuge at 4°C at 2500 x g for 15 minutes (or in accordance with centrifuge manufacturer's instructions).
- Aliquot approximately 1.0ml of plasma from each tube evenly into four 2.0ml cryovials.
- Label each cryovial with:
  - Study Number NCI9925
  - Subject ID Number
  - Sample Type Plasma
  - Collection Date
  - Collection Time
  - Frozen Time

9.4.5.1 Handling of Specimens

Plasma samples will be stored at -70°C until further use.

# 9.4.5.2 Shipping of Specimens

In the end of trial accrual, all protein marker (plasma) and pharmacogenomics (whole blood) specimens will be batched (approximately 2 batches per institution) and shipped on dry ice by courier guaranteeing overnight delivery (Monday-Thursday) to the following address:

Phase I Biomarker Laboratory ATTN: [name] Duke University Medical Center [name]

Please notify the Phase I Biomarker Laboratory ([contact]) of any incoming blood specimen shipments by providing notification two days prior to shipment via the 9925 Study Portal. The shipment notification will include upload of the Biomarker Shipment Log (see Appendix H). The 9925 Study Portal may be accessed through the following link: http://j.mp/2g4kpUG

9.4.5.4 Site Performing Correlative Studies

Protein marker analysis will be performed at the Duke Phase I Biomarker Laboratory.

# 9.4.6 Pharmacogenomics Assessment

A one-time, blood sample will be drawn prior to initiation of therapy for assessment of variants in genes anticipated to be involved in the pharmacokinetics or pharmacodynamics of nivolumab.

# 9.4.6.1 Collection of Specimens

# Whole Blood Collection and Processing:

- Draw one 6ml pink top (K2EDTA) tube (BD Vacutainer, Catalog no. 367899) at the following time point:
  - a) pre-study (i.e., baseline) only.
- Invert tube 10 times to mix blood.
- Label the tube with:
  - Study Number NCI9925
  - Sample Type Whole Blood
  - Subject ID Number
  - Collection Date
  - Collection Time
  - Frozen Time
- 9.4.6.2 Handling of Specimens

Whole blood samples will be stored at -70°C until further use.

# 9.4.6.3 Shipping of Specimens

In the end of trial accrual, all protein marker (plasma) and pharmacogenomics (whole blood) specimens will be batched (approximately 2 batches per institution) and shipped on dry ice by courier guaranteeing overnight delivery (Monday-Thursday) to the following address:

Phase I Biomarker Laboratory ATTN: [name] Duke University Medical Center [name]

- Please notify the Phase I Biomarker Laboratory ([contact]) of any incoming blood specimen shipments by providing notification two days prior to shipment via the 9925 Study Portal. The shipment notification will include upload of the Biomarker Shipment Log (see Appendix H). The 9925 Study Portal may be accessed through the following link: http://j.mp/2g4kpUG
- 9.4.6.4 Site Performing Correlative Studies

Pharmacogenomic analysis will be performed at the Duke Phase I Biomarker Laboratory.

# **10. STUDY CALENDAR**

Baseline evaluations are to be conducted within 2 weeks prior to start of protocol therapy. Scans and x-rays must be done <4 weeks prior to the start of therapy.

PROCEDURE/TEST*	Week* Cycle*										
PROCEDURE/TEST*	Pre-study	1	2	3	4	5	6	7	8	5 - 46	Off-study 
Nivolumab		Α		Α		Α		Α		Α	
Informed Consent	Х										
Demographics	Х										
Medical History	Х										
Concurrent Medications	Х	X								X	
Physical Exam	Х	Х		Х		Х		Х		Х	X
Neurological Exam 	Х	Х		Х		Х		Х		Х	X
Vital Signs	Х	Х		Х		Х		Х		Х	X
Height	Х										
Weight	Х	Х		Х		Х		Х		Х	Х
Performance Status	Х	Х		Х		Х		Х		Х	Х
HTLV Antibody Assay	Х										
CBC w/diff and Platelets	Х	Х	Х	Х	Х	Х	Х	Х	Х	Х	Х
Serum Chemistry 	Х	Х	Х	Х	Х	Х	Х	Х	Х	Х	X
Hormone Levels 	Х										
B-HCG 	Х										
EKG	Х										
Echocardiogram 	X 										
Cardiac Evaluations 		X								X	X
Adverse Event Evaluation		X								Х	X
Radiologic Evaluation	Х									12 weeks.	X
Tumor Measurements			Tum	or mea	surem	ents are	repeate	ed ever	y 12 w	eeks.	
	Х	Ε	Oocum	entation	n (radio	ologic) i	must be	provi	ded for	patients	Х
						study for	 				
Bone Marrow and Skin	Х				~ -	~	-			eline and	
Biopsy			comple	ete resp	onse (	CR) is c	btained	l by all	l other o	criteria.	
CORRELATIVE STUDIE	S										-
HTLV-1 Studies 	X 					X 				X 	X 
- PBMC											
HTLV-1 Studies 	X 										X 
- Tumor Tissue (block/core)											~~~~~~~~~~~~~~~~~~~~~~~~~~~~~~~~~~~~~~~
Immune Cell Numbers 	X 					X 				X 	X 
- Blood										21	~~~~~~~~~~~~~~~~~~~~~~~~~~~~~~~~~~~~~~~
Immune Cell Numbers 	X9										X9
- Tumor Tissue											
PD-1,-L1,-L2 Expression 	X 										X 
- Tumor tissue (slides)											
Tumor Antigen Analysis 	X 										
- Skin											

			Week*							Cycle*	
PROCEDURE/TEST*	Pre-study	1	2	3	4	5	6	7	8	5 - 46	Off-study 
Protein Markers 	X 									X 	X 
- Plasma	$X^{12}$									X12	$\mathbf{X}^{12}$
Pharmacogenomic 	3712										
- Whole Blood	X 										
*: +/- 1 day permissible for pr	ocedures, labs,	and st	udy dr	ug adm	inistra	tion					
A: Nivolumab, 240 mg every			2	0							
1: See Appendix H											
2: Albumin, alkaline phosph	atase, total bilir	ubin, t	oicarbo	onate, E	UN, c	alcium,	chlorid	e, crea	tinine,	glucose, LD	H,
phosphorus, potassium, to	tal protein, SGC	DT [AS	ST], S	GPT [A	LT], s	odium.					
3: TSH and am (i.e., before a											
4: Serum pregnancy test for					-						
5: Off-study evaluation. Fol	-			-				-		-	-
completion. However, pat	-	-							-		
develop recurrent disease											
follow up for these patient						-			-		
Adverse events assessmer	-						-				
6: Blood for PBMCs will be			•								
clonality analysis, and specifi											
then every 12 weeks thereafte	r (30mL) and at	the er	nd of s	tudy tre	eatmen	t (30ml	.). Ref	er to S	ection 9	9.4.1 for sam	ple collection
handling, and shipping.				• • • •						11 1 D 1	
7: Tumor tissue will be obtained		-	-						-		
clonality analysis, and specif		at ba	asenne	and en	a or st	udy trea	itment (	11 avai	lable).	Keter to Sec	ction 9.4.1 for
sample collection, handling, a	· · · ·		into fo		na aall	numba	ray at he		Day 1	of Cuolo 2	Day 1 of
8: Blood will be obtained at Cycle 5, and then every 12		_									
institutional standard proc		er and	i at the	end of	study	treatme	пі. ГА		issay ic	be performe	ed per
9: Tumor tissue will be obtained		vina t	ime no	vinte foi	· immu	ne cell	numhei	∘c∙ath	aceline	and at the er	d of study
treatment (if available). F											
baseline if not done prior to st	-	-		-		ionai su	illuaru	proceu	uie. Ii	ins is not req	uneu ai
10: Slides from tumor tissue	•			vanaon	.						
	will be obtained	at the	s tollos	ving tir	ne noii	nts for P	р . 1 Р	D-I.1	PD-L2	Expression:	at haseline an
at the end of study treatm	ent (if available	). Ref	fer to S	Section	9.4.3 f	or samp	le colle	ection,	handliı	ng, and shipp	oing.
at the end of study treatm 11: Skin from punch biopsy of	ent (if available collected at the s	). Ref	fer to S ime as	Section baselir	9.4.3 f ie bone	or samp marrov	le colle	ection,	handliı	ng, and shipp	oing.
at the end of study treatm 11: Skin from punch biopsy of analysis. Refer to Section	ent (if available collected at the s n 9.4.4 for collec	). Ref ame t ction,	fer to S ime as handli	Section baselin ng, and	9.4.3 f ie bond shipp	or samp e marrov ing.	ole colle w biops	ection, y will	handliı be obta	ng, and shipp ined for tum	oing. or antigen


at the end of study treatm

11: Skin from punch biopsy of analysis. Refer to Section

12: Blood for plasma will be

	ent (if available collected at the s n 9.4.4 for collected obtained at the	). Ref ame t ction, follow	fer to S ime as handli ving tir	Section baselir ng, and ne poin	9.4.3 f ie bond shippi ts for j	or samp e marrov ing. protein i	ole colle w biops markers	ection, y will at bas	handlin be obta eline (1	ng, and shipp lined for tum	or antigen ery restaging

at the end of study treatm

11: Skin from punch biopsy of analysis. Refer to Section

12: Blood for plasma will be (10mL), and at the end of

	ent (if available collected at the s n 9.4.4 for collec obtained at the study treatmen	). Ref ame t ction, follow t (10m	fer to S ime as handli ving tir nL). R	Section baselir ng, and ne poin efer to	9.4.3 f ie bond shippi ts for j Section	for samp e marrov ing. protein i n 9.4.5	ole colle w biops markers for sam	ection, y will at bas ple col	handlin be obta eline (1 lection	ng, and shipp lined for tum 10mL), at ev , handling, a	oing. or antigen ery restaging nd shipping.

 
at the end of study treatm
 
11: Skin from punch biopsy of analysis. Refer to Section
 
12: Blood for plasma will be (10mL), and at the end of
 
13: Whole blood will be obtain
 
	ent (if available collected at the s n 9.4.4 for collec obtained at the study treatmen	). Ref ame t ction, follow t (10m	fer to S ime as handli ving tir nL). R	Section baselir ng, and ne poin efer to	9.4.3 f ie bond shippi ts for j Section	for samp e marrov ing. protein i n 9.4.5	ole colle w biops markers for sam	ection, y will at bas ple col	handlin be obta eline (1 lection	ng, and shipp lined for tum 10mL), at ev , handling, a	oing. or antigen ery restaging nd shipping.

 
at the end of study treatm
 
11: Skin from punch biopsy of analysis. Refer to Section
 
12: Blood for plasma will be (10mL), and at the end of
 
13: Whole blood will be obta handling, and shipping.
 
	ent (if available collected at the s n 9.4.4 for collec obtained at the study treatmen ined at baseline	). Ref ame t ction, f follow t (10m (6mL	fer to S ime as handli ving tir hL). R ) for p	Section baselir ng, and ne poin efer to harmac	9.4.3 f ie bond shippi ts for j Section ogeno	for samp e marrov ing. protein r n 9.4.5 f mics. R	ble colle w biops markers for sam	ection, y will at bas ple col Sectio	handlin be obta eline (1 lection n 9.4.6	ng, and shipp lined for tum l0mL), at ev , handling, a for sample o	or antigen or antigen ery restaging nd shipping. collection,

 
at the end of study treatm
 
11: Skin from punch biopsy of analysis. Refer to Section
 
12: Blood for plasma will be (10mL), and at the end of
 
13: Whole blood will be obta handling, and shipping.
 
	ent (if available collected at the s n 9.4.4 for collec obtained at the study treatmen ined at baseline	). Ref came t ction, f follow t (10m (6mL stive h	fer to S ime as handli ving tir hL). R ) for p	Section baselir ng, and ne poin efer to harmac	9.4.3 f ie bond shippi ts for j Section ogeno	for samp e marrov ing. protein r n 9.4.5 f mics. R	ble colle w biops markers for sam	ection, y will at bas ple col Sectio	handlin be obta eline (1 lection n 9.4.6	ng, and shipp lined for tum l0mL), at ev , handling, a for sample o	or antigen or antigen ery restaging nd shipping. collection,

 
at the end of study treatm
 
11: Skin from punch biopsy of analysis. Refer to Section
 
12: Blood for plasma will be (10mL), and at the end of
 
13: Whole blood will be obtath handling, and shipping.
 
14: Only for patients with a base of the section of

	ent (if available collected at the s n 9.4.4 for collec obtained at the study treatmen ined at baseline history of conges rugs as clinicall	). Ref ame t ction, follow t (10m (6mL stive h y indic	fer to S ime as handli ving tir hL). R ) for p heart fa cated.	Section baselir ng, and ne poin efer to harmac ilure or	9.4.3 f e bond shippi ts for p Section ogeno	or samp e marrov ing. protein 1 n 9.4.5 mics. R	ble colle w biops markers for sam efer to the of un	ection, y will at bas ple col Sectio derlyir	handlin be obta eline (1 lection n 9.4.6 ng cardi	ng, and shipp lined for tum (0mL), at ev , handling, a for sample o iovascular di	ving. or antigen ery restaging nd shipping. collection, sease or

